## **4.3 Data Management**

Electronic CRFs will be used to capture study results and data. Staff at the SKCCC Coordinating Center will be responsible for the initial study configuration and setup of the database and for any future changes. The site study coordinator or other authorized study

personnel will transcribe data from source documents onto the eCRFs. Site Investigators will be responsible for ensuring that data entry into the eCRFs are kept up-to-date. Before or between visits, the Protocol Chair, IND Sponsor, or designee may request copies of the source documents for preliminary medical review and quality assurance. Once the eCRFs are complete and source-verified, the investigator may sign and verify the accuracy of all data contained within the EDC.

#### **4.3.1 Case report forms completion**

eCRFs will be completed within 2 weeks of the patient coming to the clinic and all relevant supporting documentation such as scans, progress notes, nursing notes, blood work, pathology reports, etc., will be submitted via email to the SKCCC Coordinating Center Study Manager. All patient names and other identifying information will be removed prior to being sent to the Coordinating Center or non-redacted source documents can be sent via a password-protected/ secured document transfer based on each institution's guidelines.

#### **4.3.2 Source documents**

Source documentation will be maintained by site study staff to support the patient research record. SKCCC Study Manager and/or Monitors will remotely review entries on the CRFs at regular intervals, comparing the content with source documents.

#### **4.3.3 Record retention**

The investigator will maintain adequate and accurate records to enable the conduct of the study to be fully documented and the study data to be subsequently verified. After study closure, the investigator will maintain all source documents, study-related documents, and the CRFs. Because the length of time required for retaining records depends upon a number of regulatory and legal factors, documents should be stored until the investigator is notified that the documents may be destroyed. In this study, records are to be retained and securely stored for a minimum of 7 years after the completion of all study activities.

### **4.4 Study Monitoring and Quality Assurance**

All clinical work conducted under this protocol is subject to Good Clinical Practice (GCP) guidelines. This includes inspection of study-related records by the lead site, investigator-sponsor, its designee, or health authority representatives at any time.

Remote data monitoring will occur on a regular basis with the frequency dependent on the rate of subject accrual and the progress of the study. The protocol will be monitored internally at SKCCC by the SKCCC Clinical Research Office Quality Assurance Core (CROQA), and externally at participating institutions by the SKCCC Study Manager.

Regularly scheduled reports will be generated from the eCRFs to monitor patient accruals and the completeness of research data. Routine data quality reports will be generated to assess missing data and inconsistencies. Accrual rates and the extent and accuracy of evaluations and follow-up will be monitored periodically throughout the study period, and potential problems will be brought to the attention of the principal investigator for discussion and action.

#### **4.4.1 Data and Safety Monitoring**

This is a JHU-investigator-sponsored IND trial. Data and safety monitoring will follow DSMP Level 2 per the SKCCC Data Safety Monitoring Plan. The PI shall internally monitor the progress of the trial, including review and confirmation of all safety/treatment-related outcomes, response assessments, safety reports and/or any related source documentation. PI shall also establish additional external data/safety monitoring oversight (DSMB, etc), if required by IND-sponsor and detailed within protocol. IND-sponsor is ultimately responsible for external monitoring of JHU site, and also all subsites if JHU is coordinating center. Authorized representatives of the Coordinating Center may visit the satellite sites to perform audits or inspections, including source data verification. The purpose of these audits or inspections is to systematically and independently examine all trial-related activities and documents to determine whether these activities were conducted and data were recorded, analyzed, and accurately reported according to the protocol, Good Clinical Practice (GCP), and any applicable regulatory requirements.

The Data Safety Monitoring Board (DSMB) for this clinical study will contain a minimum of five members, including at least one oncologist, a statistician, and a lay representative. Members may not have a conflict of interest with any aspect of the clinical trial. The DSMB will provide a written recommendation to the IND Sponsor and Protocol Chair after each meeting. In turn, the study team will forward these summaries to the JHU IRB, and JHU SKCCC SMC. The operating plan of the DSMB will be as follows:

- Meetings will be held at least semi-annually, and potentially more frequently if needed.
- Meetings will be conducted in-person or via video/teleconference, with a participant sign-in sheet collected at each meeting. The Protocol Chair and study staff may attend the open portion of this meeting to review data and answer any question the DSMB might have).
- Approximately one week prior to each DSMB meeting, the study team will submit the following items to DSMB members for review and discussion at the meeting:
  - A summary of the clinical trial's progress to date;
  - The latest IRB-approved protocol and informed consent;
  - A summary of all adverse events, serious adverse events, deaths, and withdrawals to date;

Note that the DSMB may recommend halting trial accrual or all study activity if, after review, serious safety concerns warrant this action. If the DSMB recommends halting study accrual or all study activity, then the study team must notify the JHU SKCCC SMC, JHU IRB, and the FDA immediately.

## **5. TREATMENT PLAN**

This is a randomized, double-blind, placebo controlled multicenter study to compare the change in slope and PSADT from baseline between placebo and MDX treatment groups. Approximately 500 subjects will be registered and genotyped to find 80 men with AA genotype for enrollment.

Those with AA genotype will be enrolled and randomized 1:1 (40 to placebo and 40 to MPX). Treatment on study will last 48 weeks and will be administered on an outpatient basis.

Appropriate dose delays and discontinuation recommendations for MPX are described in Section 6. Adverse event reporting requirements and potential risks are described in Section 7. No investigational or commercial agents or therapies other than those described below may be administered with the intent to treat the patient's malignancy.

### **5.1 MPX Administration**

Each treatment cycle is 12 weeks (84 days). Patients will take 8 MPX pills or 8 placebo pills daily, for once daily oral dosing of 4000 mg MPX. Patients may continue to receive additional cycles of study drug and will be followed every 12 weeks with standard visits with their physician until completion of 48 weeks of study treatment, disease progression, or until they wish to discontinue the drug.

Patients will self-administer the assigned number of capsules on a daily schedule. Patients will return capsule containers and any unused study drug to the study coordinator or research nurse at each scheduled follow-up visits. Returns will be documented on the drug accountability log by the pharmacist or pharmacist designee.

Compliance with study product consumption will be evaluated by subject interview and by patient pill diaries (Appendix B) that will be collected at each visit. Compliance will be recorded as a percent of scheduled intakes of study product consumed. Non-compliance will be defined as consumption of <80% of the scheduled intakes of study product.

Patients will be asked to refrain from adding other vitamin or herbal supplements during the study period and follow-up. If a patient does not comply, he will first be counseled that he may be withdrawn from the study. If he persists in taking vitamins or herbal supplements, he will be withdrawn from the study.

Participants will be encouraged to administer the MPX capsules as follows:

- 1) MPX Capsules must be swallowed whole
- 2) MPX Capsules should be taken with water
- 3) MPX capsules should be taken at least 60 minutes prior to eating or 2 hours after eating
- 4) Ingestion of capsules may be spread out over 2 hours if necessary
- 5) Vomited doses will not be made up. If the vomiting occurs after 3 sequential doses and is thought to be related to study drug, the patient should refrain from taking additional MPX capsules and report this to study team.
- 6) If a dose is missed (forgotten at the usually administered time), it may be made up any time later that same day.

### **5.2 Blinding**

The double-blind portion of the study will end when every subject has either completed the study, been treated for 48 weeks, or discontinued the study. A subject is considered to have completed the study if he experiences PSA progression as defined in section 5.4. A subject will also be considered to have completed the study if they have not experienced PSA progression but remain on-study at the time the study ends at 48 weeks. Patients will not be informed if they are on the MPX or placebo arm. At protocol defined progression or completion of 48 weeks of treatment, patients will be offered an additional four 12-week cycles of MPX treatment, and will come for a visit every 12 weeks, without correlates but with PSA drawn every 12 weeks. Patients who come off study for any other reason will not be offered open label, extension MPX. Subjects will have an end of study visit and are required to have CT and bone scans prior to beginning the open label extension, and at discharge.

### **5.3 General Concomitant Medication and Supportive Care Guidelines**

Patients may not be taking any other medications for the goal of treating their prostate cancer. If they are taking medications for other purposes, they may continue per the guidance of the doctor.

Patients who have an on-going study drug-related serious adverse event upon study completion or at discontinuation from the study will be contacted by the investigator or his/her designee periodically until the event is resolved or determined to be irreversible.

### **5.4 Definition of Treatment Response and Disease Progression**

**Objective Response (OR):** Defined as a decrease of 50% or more in the PSA compared with the baseline level, confirmed by a second PSA at least 3-4 weeks later.

**Progressive Disease (PD):** Defined as:

- Radiographic Progression  
Radiographic progression for soft tissue lesions will be determined using RECIST 1.1. Radiographic progression for bone lesions will be determined by radionuclide bone scan using the consensus guidelines of the PCWG2 criteria, Or
- Unequivocal clinical progression: physical symptoms felt to be cancer related (in the opinion of the investigator), Or
- PSA Progression: Clinically significant increase in PSA as defined below.
  - *For subjects whose PSA declined from baseline (week 1 day 0):* record time from start of therapy to first PSA increase that is  $\geq 50\%$  and  $\geq 5$  ng/mL above the nadir, and which is confirmed by a second value  $\geq 3$  weeks later.
  - *For subjects whose PSA has not declined from baseline:* PSA progression has occurred if both:  
There has been a  $> 50\%$  increase over baseline (week 1 day 0), AND  
The value of PSA is  $> 5$  ng/mL above the baseline (week 1 day 0) value after 12 weeks

If subject's PSA progresses  $\geq 50\%$  and  $\geq 5$  ng/mL above the baseline (week 1 day 0) on Week 12, repeat the PSA at Week 14-16 to confirm rise. Subjects should continue taking study drug during this period, until the rise is confirmed. Once confirmed, subjects should either schedule Discontinuation Visit or start Open Label Extension treatment.

**Stable Disease (SD):** Disease Assessment that does not qualify as either objective response or progressive disease.

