## **11.2 Secondary Efficacy Assessment**

**PSA Doubling Time (PSADT):** The PSADT will be calculated as  $\ln(2)$  ( $=0.693$ ) /  $\beta$  ( $=$ slope of the linear regression fit to  $\ln$  PSA vs. time in months). If the patient's slope is less than or equal to zero, we will assign them a PSADT of 100 months, which is consistent with the literature.

A secondary statistical test of the difference between the two groups will be assessed by a nonparametric Wilcoxon Rank Sum test of the percentage change in PSADT (logarithm of the ratio of PSADT on-study divided by the pre-treatment PSADT). We will also analyze the log of the PSADT ratio by the analysis of variance (ANOVA) adjusted for the stratification factors. Confidence intervals (95%) for the change from baseline in PSADT will also be computed for the two dose groups. The paired t-test (or Wilcoxon signed-rank test) will be used to assess the within treatment group differences of PSADT on study compared to the baseline. Patients with negative slopes will be assigned PSADT of 100 months.

**PSA Reduction of  $\geq 50\%$  / Objective Response:** An objective response (OR) is defined as a decrease in PSA by 50% or more after the start of treatment. The objective response rate (ORR) is estimated as the fraction of men for whom an objective response is observed. The time to objective response, defined as the time from start of treatment to an observed objective response, as well as the average duration of response, defined as the time from objective response to disease progression, will also be summarized and compared between groups. To further summarize PSA responses, the percentage change in PSA from baseline at 24 and 48 weeks will be presented in the form of waterfall plots.

**PSA Progression:** The distribution of time to PSA progression will be estimated using Kaplan-Meier method for both treatment groups combined and separately. The stratified logrank test will be used to test the hypothesis that the time to PSA progression distributions for the 2 treatment groups are the same. The same stratification factors used for the randomization will be used to stratify the logrank test.

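### Section 5.4 writes no confirming PSA for men whose PSA never declined and who first cross at week 24, 36 or 48, so the PSA-progression event is defined differently according to a post-randomisation PSA decline

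*Combined protocol and SAP*

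**What the plan says.** Section 5.4 contains three PSA rules.

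- **PSA declined from baseline.** A rise of at least 50% and at least 5 ng/mL above the nadir counts only if it meets the condition "and which is confirmed by a second value" at least 3 weeks later. No visit is singled out.
- **PSA never declined.** Under "For subjects whose PSA has not declined from baseline", the text says "PSA progression has occurred if both" thresholds are passed: more than 50% over baseline, and more than 5 ng/mL above the baseline "value after 12 weeks". No second value is mentioned.
- **Week 12.** If the rise is at least 50% and at least 5 ng/mL above baseline "on Week 12, repeat the PSA at Week 14-16 to confirm rise". Study drug continues meanwhile, and then: "Once confirmed, subjects should either schedule Discontinuation Visit or start Open Label Extension treatment".

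The progression call has two uses. Section 5.2 states: "At protocol defined progression or completion of 48 weeks of treatment, patients will be offered an additional four 12-week cycles of MPX treatment". Calendar footnote 7 makes Section 5.4 progression the only way into the extension before week 48 and excludes radiographic progression. Section 11.2 states: "The distribution of time to PSA progression will be estimated using Kaplan-Meier method", with a stratified log-rank comparison of the arms. It adds no confirmation rule of its own.

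**The concern.** Two men with the same rise at week 24 are handled differently. If one had a slightly lower PSA at week 12, his rise must be confirmed. If the other's PSA never dipped, he has progressed on a single value. The dividing line is a PSA decline after randomisation, which treatment is meant to influence, so the event in a randomised log-rank comparison is not defined the same way for everyone.

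The same single value can end blinded treatment before week 48 and start open-label MPX, including for a man on placebo. It also cuts the on-study PSA series used for the primary slope from five values to three (call at week 24) or four (call at week 36), and the last value was selected for being high.

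There are smaller inconsistencies in the same section. The thresholds are strict in the never-declined rule and non-strict in the week-12 rule. A week-14 repeat falls 2 weeks after week 12, short of the 3 weeks asked of decliners. The reference to 12 weeks in the never-declined rule can mean at that visit or from then on.

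**Working it through.** **1. Is confirmation supplied elsewhere?** The documents state no number or timing of PSA progressions, so there is no plan figure to reproduce. The text gives:

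| First crossing | PSA declined earlier | PSA never declined |
|---|---|---|
| Week 12 | repeat required | repeat at weeks 14-16 |
| Weeks 24, 36, 48 | repeat at least 3 weeks later | none written |

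Sections 5.2 and 5.5, the calendar footnotes and Section 11.2 do not fill the empty cell.

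**2. When do crossings occur?** A 50% rise by time *t* needs PSADT of at most *t* × ln 2 / ln 1.5. Week 12 is 84/30.44 = 2.76 months, so the limit is 2.76 × 0.693/0.405 = 4.7 months. The limits at weeks 24, 36 and 48 are 9.4, 14.2 and 18.9 months. Section 11 expects average PSADT of 6 to 15 months. At 6 months, growth by week 12 is 2^(2.76/6) − 1 = 38%, short of 50%. The average man therefore cannot cross until after week 12. Individuals can: 50% by week 12 is a slope of 0.405/2.76 = 0.147 per month, and with the plan's placebo mean 0.083 and SD 0.075 about 1 − Φ(0.85) = 20% of placebo men exceed it. They must also meet the 5 ng/mL criterion.

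**3. How many calls are unconfirmed?** This needs simulation.

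- From Section 11: mean on-study log slopes 0.033 (MPX) and 0.083 (placebo) per month, SD 0.075.
- Assumed, because the documents give neither: log-normal baseline PSA with median 2, 5 or 10 ng/mL and log SD 1; log-PSA noise SD 0.10 or 0.20.
- 400,000 men per arm and scenario, PSA at day 0 and weeks 12, 24, 36 and 48, no dropout, Section 5.4 thresholds applied, and a notional repeat 28 days after each crossing.

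Never-decliner calls at weeks 24-48 as a share of all first crossings, arms pooled:

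| Median baseline PSA | Noise 0.10 | Noise 0.20 |
|---|---|---|
| 2 ng/mL | 91% | 76% |
| 5 ng/mL | 82% | 62% |
| 10 ng/mL | 75% | 52% |

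The lowest single-arm value is 51%. Of these calls, the 28-day repeat falls below threshold in about 6-18% on placebo and 9-25% on MPX. Restricted to weeks 24 and 36, where the call also ends blinded treatment early, that is about 0.4-2.3 men per 40-man arm. The arms differ by about half a man at most.

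**4. Is one arm held to the stricter rule more often?** Decliners who later cross are about 0.7-13.5% of men in either arm. Within a scenario the arms differ by about 1 percentage point at most.

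**5. The primary slope.** Section 11.1 needs at least three on-study values. A man called at week 24 has day 0, week 12 and week 24, so he stays in the analysis with a shorter and noisier series.

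**The case against.** The sponsor may have meant the confirmation wording in the week-12 paragraph to cover every visit. That is possible, but the paragraph names only week 12, and if all visits were intended the text still has to say so.

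The stronger objections concern size, and most of them stand. The endpoint is secondary, and Section 11.4 treats everything except the primary outcome as secondary, tertiary or exploratory. The number of early calls that a repeat would overturn is small and similar between arms. A week-48 call coincides with completion and truncates no blinded series. No effect on the log-rank test or on the primary slope has been estimated.

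Four stronger readings are tempting and are not supported:

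- *Most switches to open-label MPX rest on one value.* Sections 5.2 and 5.5 offer the extension to men who complete 48 weeks, whatever their PSA. Even with median baseline PSA varied from 0.5 to 10 ng/mL and noise from 5% to 20%, unconfirmed calls at weeks 24 and 36 involved only about 3-36% of all men.
- *The stricter rule falls mainly on MPX.* The plan's inputs imply negative slopes in Φ(−0.033/0.075) = 33% of MPX men and Φ(−0.083/0.075) = 13% of placebo men. Men with falling PSA seldom progress, though, so a confirmation rule seldom touches them. Step 4 shows near-equal numbers where it does.
- *A week-12 crossing requires a baseline PSA of at least 10.* That is only where the 50% and 5 ng/mL limits coincide. With PSADT of 3 months, growth is 2^(2.76/3) = 1.89-fold and a baseline of about 5/0.89 = 5.6 suffices.
- *The primary analysis loses these men.* It does not (step 5).

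**Conclusion.** The gap is in the text and does not depend on any assumption: never-decliners who first cross at weeks 24, 36 or 48 have no written confirmation step, while decliners at any visit and all men at week 12 do. The mixed inequality signs and the short week-14 interval are equally plain. As written, the time-to-PSA-progression event depends on post-randomisation PSA behaviour, and a PSA-based exit before week 48 can rest on one value.

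That these calls are the majority of PSA progressions held in every scenario run, but it rests on an assumed baseline PSA distribution and assumed noise. The expected harm is added noise in a secondary endpoint and some shortened PSA series. A demonstrated bias between arms is not part of the conclusion. The text should be corrected, but the point does not threaten the trial's primary conclusion.

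**What to change.** For the Section 11.2 time-to-PSA-progression analysis, state one event definition for decliners and never-decliners at every visit: the same confirmation requirement, the same inequality signs, and the event dated at the first qualifying value. Say explicitly how a first crossing at week 48 is counted, since no blinded visit follows it.

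Separately, ask the sponsor to reconcile the Section 5.4 paragraphs with each other, and with Sections 5.2 and 5.5 and the calendar footnotes, on when a PSA rise counts as progression. The clinical rule for stopping blinded drug or starting open-label MPX is for the sponsor to state consistently; none is proposed here.

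The cost is protocol and analysis wording, plus one repeat PSA for men who cross. The downside is slightly fewer, or later-ascertained, PSA-progression events.

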## 5.5 Duration of Therapy

Patients may continue on blinded therapy for up to 48 weeks.

Patients may be removed from the study if any of the following occurs.

- Completion of 48 weeks of study therapy
- Disease progression (see Section 5.4)
- A new illness that prevents further administration of treatment
- Unacceptable adverse event(s)
- Patient decides to withdraw from the study
- General or specific changes in the patient's condition that renders the patient unacceptable for further treatment in the judgment of the investigator
- Noncompliance: Subjects who do not meet 80% dosing compliance will be counseled, if they are deemed non-compliant at their next visit they will be withdrawn from the study

Patients who complete all protocol requirements will be offered an additional 48 weeks of MPX treatment and monitoring every 12 weeks as the Open Label Extension.

